11. MEASUREMENT OF EFFECT

11.1 Antitumor Effect – Solid Tumors

Although response is not the primary endpoint of this trial, patients with measurable disease will be assessed by standard criteria. For the purposes of this study, patients should be re-evaluated for response every 8 weeks (every 2 cycles; 3 cycles for patients on study for a year). In addition to a baseline scan, confirmatory scans should also be obtained at least 4 weeks following initial documentation of objective response.

Response and progression will be evaluated in this study using the new international criteria proposed by the revised Response Evaluation Criteria in Solid Tumors (RECIST) guideline (version 1.1) [*Eur J Ca* 45:228-247, 2009]. Changes in the largest diameter (unidimensional measurement) of the tumor lesions and the shortest diameter in the case of malignant lymph nodes are used in the RECIST criteria.

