3.4 Screening Evaluation

- 3.4.1 Histologic confirmation: All patients are required to have histologically confirmed solid tumor(s) per Sections [3.1.1](#) or [3.1.2](#). Pathology confirmation should preferably be done by the Laboratory of Pathology, NIH. However, pathology reports from outside institutions confirming the diagnosis will also be acceptable for eligibility purposes.
- 3.4.2 History and physical examination: Complete history and physical examination (including height, weight, vital signs, performance score, EKG) will be conducted within 8 days prior to enrollment.
- 3.4.3 Imaging Studies (Baseline): Every participant should have an evaluation of known sites of disease as part of the baseline evaluation. All patients will be required to undergo a CT scan of the chest/abdomen/pelvis to evaluate sites of disease within 28 days prior to enrollment. In an occasional patient, MRI may be performed for a disease site instead of a CT scan if MRI is felt to provide more accurate measure of disease. MRI or CT scan with contrast of the brain, MRI liver, MRI for other disease sites, or bone scan may be done as clinically indicated.

3.4.4 Laboratory Evaluation: Baseline laboratory data are to be obtained within 8 days prior to enrollment:

- Hematological Profile: CBC with differential.
- Biochemical Profile: albumin, alkaline phosphatase, total bilirubin, BUN, calcium, creatinine, phosphorus, total protein, SGOT[AST], SGPT[ALT], magnesium, potassium, LDH, and sodium.
- Coagulation Profile: PT, PTT, INR for patients undergoing tumor biopsy.
- Urine and/or serum pregnancy test for female participants of childbearing potential.
- Erythrocyte analyses per [Appendix F](#).

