5. TREATMENT PLAN

Phase I: This is an open-label Phase I trial evaluating the combination of oral TRC102 with oral TMZ, in 28-day cycles. The starting dose of TRC102 is based on the safety information from the trial of IV TRC102 combined with TMZ. The study will follow a 3+3 design: dose will be escalated in cohorts of 3 patients with the individual dose of TRC102 and TMZ increased in successive dose levels as outlined in the dose escalation table below. Once the MTD is established, up to 15 additional patients will be enrolled at the MTD (expansion phase) to further define the dose and evaluate PK and PD at this dose level.

Phase II: Patients with a body surface area (BSA) of $\geq 1.6 \text{ m}^2$ will be started on 125 mg TRC 102 and 150 mg/m² Temozolomide orally on days 1-5 of each 28-day cycle (DL6). Patients with a BSA of $< 1.6 \text{ m}^2$ will be started on 100 mg TRC 102 and 150 mg/m² Temozolomide orally on days 1-5 of each 28-day cycle (DL5). There will be no dose escalation for patients on the Phase II portion of the study; appropriate dose modifications are described in [Section 6](#). Up to 75 patients will be accrued to this part of the study.

History and physical examination can be done up to 8 days before start of a new cycle. Patients will be examined at baseline for the first cycle then at the start of every cycle for the remainder of the study (up to 3 days before start of a new cycle). The start of the next cycle may be delayed for up to 1 week to accommodate scheduling conflicts.

Labs (CBC with differential; serum chemistries) will be performed (+/- 2 days) as follows: every week up to week 3 for cycle 1. Starting with cycle 2, labs (CBC with differential; serum chemistries) will only be performed before the start of each cycle (laboratory evaluation may be performed up to 7 days prior to scheduled date to accommodate scheduling conflicts and patient convenience). If clinically indicated, labs may be obtained more frequently.

Blood for erythrocyte analysis (optional) will be collected on cycle 1 days 7, 14, and 21 (+/- 2 days) as described in [Appendix F](#).

CT scans will be performed at baseline, and repeat scans will be performed every 2 cycles (every 3 cycles for patients on study more than one year).

Phase I Dose Escalation Schedule (28-day cycle)		
Dose Level	TRC 102 orally	TMZ orally
Level -2	25 mg once daily D1-5	75 mg/m ² once daily D1-5
Level -1	25 mg once daily D1-5	100 mg/m ² once daily D1-5

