6. DOSING DELAYS/DOSE MODIFICATIONS

Non-hematologic toxicities (at least possibly related to therapy) should have resolved to \leq Grade 1 or baseline prior to starting the next cycle or receiving the next dose of TRC102 or TMZ within a cycle. Grade 2 electrolyte abnormalities, grade 2 nausea/vomiting/diarrhea in the absence of maximal palliative support, or any grade alopecia, will not result in holding or delaying study drugs.

Hematologic toxicities (at least possibly related to therapy) should have resolved to \leq Grade 1 for thrombocytopenia, \leq Grade 2 for neutropenia and anemia prior to resuming therapy except any grade lymphopenia, leucopenia in the absence of grade 3 neutropenia.

Even though study drug administration is allowed at these lower grades, every effort should be made to correct the abnormal lab values to normal if possible. If the potassium level is grade 2 or greater and/or if the calcium, magnesium, and/or phosphate are grade 3 or higher, an EKG must be performed and appropriate action taken based on the results.

Treatment may be delayed for a maximum of 2 weeks for toxicities. In case toxicities do not resolve as stated, the patient will not receive further therapy on this protocol and will be followed for resolution of toxicities. Start of next cycle may be delayed for up to 1 week to accommodate scheduling conflicts. Dose modifications are intended for within-cycle and start-of-next-cycle changes.

A maximum of 2 dose reductions will be allowed before patient is taken off treatment. Patients who require a dose reduction will not have the dose re-escalated. For patients who had one dose reduction without significant change in their toxicities (i.e., fatigue), they could be dose reduced to 4 days of the same dose level instead of dropping to the next lower dose level.

Patients will be carefully monitored for evidence of liver toxicity and toxicity will be graded per CTCAE criteria ([Section 7.2](#)). For patients who develop grade 3 LFT abnormalities, study drugs will be held and the benefits and risks of continuing treatment on a reduced dose will be discussed with the patient by the study team.

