Tumor biopsies are optional during the escalation phase but mandatory for the 15 additional patients enrolled at the MTD during the expansion phase and Phase II portion of the study. Baseline biopsies will be performed following patient enrolling on study or if the patient had a biopsy within the past 3 months and had no treatment since that biopsy, an attempt will be made to obtain and process that tissue as baseline biopsy. If the tissue could not be used for planned PD studies, a biopsy will be performed. If an initial attempt at biopsy is unsuccessful, the patient will be given an option to proceed with a repeated attempt. A separate consent form must be signed for each biopsy procedure, so patients may choose not to undergo subsequent biopsies. If the baseline biopsy is unsuccessful or the patient refuses to undergo subsequent biopsies, no further biopsies will be performed but the patient will remain on study, receive study medication, and other correlative studies will be performed. The patient will be replaced in the accrual scheme of the expansion phase.

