10. STUDY CALENDAR

Baseline evaluations are to be conducted within 8 days prior to start of protocol therapy. Scans and x-rays must be done \leq 4 weeks prior to the start of therapy. In the event that the patient's condition is deteriorating, laboratory evaluations should be repeated within 48 hours prior to initiation of the next cycle of therapy. Start of next cycle may be delayed for up to 1 week to accommodate scheduling conflicts. History and physical examination and laboratory evaluations can be performed up to 1 week before the start of the next cycle.

	Pre-Study	C1 W1	C1 W2 ^k	C1 W3 ^k	C1 W4 ^k	C2 W1 ^k	C2 W3	C3 W1 ^k	C3 W3 ^k on	Off Treatment ^j
TRC102/TMZ ^a		X				X		X		
Informed consent	X									
Demographics	X									
Medical history	X					X		X		
Concurrent meds	X	X-----						X		
Physical exam ^b	X	X				X		X		X

Vital signs	X					X		X		X
Height	X									
Weight	X					X		X		X
Performance status	X					X		X		X
CBC w/diff, plts ^c	X		X	X		X		X		
Serum chemistry ^c	X		X	X		X		X		
Anemia ^l	X	X	X							
PT, INR, PTT ^d	X									
β-HCG ^e	X									
AE evaluation			X-----X							X
Tumor measurements	X		Tumor measurements are repeated every 2 cycles (3 cycles for patients on study more than 1 year). Documentation (radiologic) must be provided for patients removed from study for progressive disease.							
Tumor biopsy ^f	X	X								
PK blood ^g		X								
Circulating tumor cells ^h		X				X				X
ECG ⁱ	X									

a: TRC102 and TMZ will be administered once daily, days 1-5, in 28 day cycles.
b: Physical exam at the Clinical Center should be performed at the start of each cycle (up to 1 week before start of a new cycle). Start of the next cycle may be delayed for up to 1 week to accommodate scheduling conflicts.
c: Serum chemistry (albumin, total bilirubin, calcium, creatinine, phosphorus, magnesium, potassium, sodium, SGOT [AST], SGPT [ALT], LDH); CBC w/diff, platelets up to week 3 during cycle 1 (Phase I only), and during week 1 in cycle 2 and subsequent cycles (up to 1 week before start of a new cycle) (Phase I and II). If clinically indicated, labs may be obtained more frequently.
d. PT/INR, PTT as clinically indicated.
e: Serum pregnancy test (women of childbearing potential) within 8 days prior to enrollment and as clinically indicated.

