11.1.3 Guidelines for Evaluation of Measurable Disease

All measurements should be taken and recorded in metric notation using a ruler or calipers. All baseline evaluations should be performed as closely as possible to the beginning of treatment and never more than 4 weeks before the beginning of the treatment.

The same method of assessment and the same technique should be used to characterize each identified and reported lesion at baseline and during follow-up. Imaging-based evaluation is preferred to evaluation by clinical examination unless the lesion(s) being followed cannot be imaged but are assessable by clinical exam.

Clinical lesions: Clinical lesions will only be considered measurable when they are superficial (e.g., skin nodules and palpable lymph nodes) and ≥ 10 mm diameter as assessed using calipers (e.g., skin nodules). In the case of skin lesions, documentation by color photography, including a ruler to estimate the size of the lesion, is recommended.

Chest x-ray: Lesions on chest x-ray are acceptable as measurable lesions when they are clearly defined and surrounded by aerated lung. However, CT is preferable.

Conventional CT and MRI: This guideline has defined measurability of lesions on CT scan based on the assumption that CT slice thickness is 5 mm or less. If CT scans have slice thickness greater than 5 mm, the minimum size for a measurable lesion should be twice the slice thickness. MRI is also acceptable in certain situations (e.g., for body scans).

As with CT, if an MRI is performed, the technical specifications of the scanning sequences used should be optimized for the evaluation of the type and site of disease. Furthermore, as with CT, the modality used at follow-up should be the same as was used at baseline and the lesions should be measured/assessed on the same pulse sequence. It is beyond the scope of the RECIST guidelines to prescribe specific MRI pulse sequence parameters for all scanners, body parts, and diseases. Ideally, the same type of scanner should be used and the image acquisition protocol should be followed as closely as possible to prior scans. Body scans should be performed with breath-hold scanning techniques, if possible.

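### Restaging is set at both 8 weeks and 2 cycles, which part once a cycle is delayed; scans should be counted from cycle 1 day 1.

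*Combined protocol and SAP*

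**What the plan says.** **Restaging.** Section 11.1 states that "patients should be re-evaluated for response every 8 weeks (every 2 cycles; 3 cycles for patients on study for a year"). It gives a calendar interval and a cycle count as if they were the same. Section 5 says only that "repeat scans will be performed every 2 cycles", moving to every 3 cycles after one year, and the calendar in Section 10 also counts cycles only.

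**Delays.** Section 6.1 defines a cycle as 28 days from the first dose of that cycle. Section 6 says "Treatment may be delayed for a maximum of 2 weeks for toxicities" and separately allows the next cycle to start up to 1 week late for scheduling. I found no limit on how many cycles may be delayed, no statement on whether the two kinds of delay can add up, and no rule on what happens to the scan date when a cycle slips.

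**Endpoints.** The only secondary objective (Section 1.2) is to explore the PFS rate in the three Phase II cohorts. Section 11.1.5 ends a response on the first date that progression is objectively documented. I found no separate PFS definition and no landmark time, and Section 13 attaches no test or threshold to PFS.

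**Baseline scan.** Section 3.4.3 asks for imaging "to evaluate sites of disease within 28 days prior to enrollment". The calendar counts "4 weeks prior to the start of therapy", and Section 11.1.3 says "never more than 4 weeks before the beginning of the treatment".

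**The concern.** Progression found by imaging is dated by the scan that shows it, so the scan schedule is part of the endpoint. If scans follow cycles and cycles follow tolerance, patients held for toxicity are imaged less often and their progression is recorded later, although their disease is no different. Such delays are foreseeable: Section 2.5 names hemolytic anemia as the dose-limiting toxicity in Phase I, and Section 6 requires blood counts to recover before treatment resumes.

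The cohorts are single-arm, so a delay of this kind does not cancel against a control group. At stake are the PFS rate, the duration of response and consistency between patients: two patients handled correctly under different sections could be scanned up to 4 weeks apart.

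**Working it through.** **1. The plan's own figure.** 2 cycles × 28 days = 56 days = 8 weeks, so the equation in Section 11.1 holds without delay. After one year, 3 × 28 days = 84 days = 12 weeks.

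**2. First restaging under cycle counting.** Let *d* be the delay in weeks at each cycle start after the first. *d* = 1 is the scheduling limit and *d* = 2 the toxicity limit, the latter read as applying to each delay. The text does not say whether the scan falls at completion of cycle 2 or at the start of cycle 3.

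- At completion of cycle 2: 4 + *d* + 4 = 8 + *d*. This is week 9 for *d* = 1 and week 10 for *d* = 2.
- At the start of cycle 3: 2 × (4 + *d*) = 8 + 2*d*. This is week 10 for *d* = 1 and week 12 for *d* = 2.

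**3. Later restaging.** From one restaging to the next there are two cycles and two delays: 2 × (4 + *d*), or 10 weeks for *d* = 1 and 12 weeks for *d* = 2. With *d* = 2 throughout, the second restaging falls at 4 × 4 + 3 × 2 = week 22 (completion) or 4 × 4 + 4 × 2 = week 24 (next cycle start), against week 16 without delay. After one year, 3 × (4 + *d*) gives 15 or 18 weeks instead of 12.

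**4. Effect on the recorded time of progression.** The documents give no PFS assumption, so I assume exponential times to progression with true medians *m* of 8 to 26 weeks, rate λ = ln 2 / *m*, and detection only at scans. For a constant interval *I*, the mean recorded time is *I* / (1 − exp(−λ*I*)). For a first scan at week 10 and every 12 weeks after, it is 10 + 12 × exp(−10λ) / (1 − exp(−12λ)).

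| *m* (weeks) | Every 8 weeks | Every 12 weeks | Shift | Week 10, then every 12 | Shift |
|---|---|---|---|---|---|
| 8 | 16.00 | 18.56 | 2.56 | 17.80 | 1.80 |
| 12 | 21.62 | 24.00 | 2.38 | 23.47 | 1.85 |
| 16 | 27.31 | 29.60 | 2.29 | 29.19 | 1.88 |
| 26 | 41.65 | 43.83 | 2.18 | 43.57 | 1.92 |

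With the maximum toxicity delay at every cycle start, progression is recorded 1.8 to 2.6 weeks later on average.

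**5. Effect on a PFS rate.** At a landmark *T* the recorded rate is exp(−λ × last scan at or before *T*). The plan states no landmark, so take week 26 and *m* = 12 as an illustration:

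- 8-week scans: last scan at week 24, rate 0.250.
- 12-week scans: last scan also at week 24, rate 0.250.
- 10-week scans: last scan at week 20, rate 0.315.
- Week 10, then every 12: last scan at week 22, rate 0.281.

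The true rate is 0.223. The distortion of a rate depends on how the scans fall around the landmark and can be nil.

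**6. Baseline scan.** A scan taken before enrollment and no more than 28 days before first dose meets Sections 3.4.3, 10 and 11.1.3 together. A scan that meets 3.4.3 but is more than 4 weeks old at first dose breaches Sections 10 and 11.1.3. The rules have different anchors, but the stricter one is written down twice.

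**The case against.** **The 8-week wording may govern.** Section 11.1 is the measurement section and it says 8 weeks. If sites follow it literally, none of the delay arises. That is true, but nothing says that it takes precedence over Section 5 and the calendar, and its own parenthesis points back to cycles. The ambiguity stands; the delay is conditional on how it is resolved.

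**The extreme is a corner case.** Repeated maximum delays are unlikely. Section 6.1 sends most related grade 3–4 toxicities to a lower dose level, and Section 6 allows only two reductions before treatment ends. The documents give no frequency of delays, and reading the 2-week limit as per delay is an interpretation. This stands, so the figures above are ceilings.

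**PFS carries no decision.** It is exploratory and has no threshold. This also stands. A reader might infer that the delay threatens the Simon decisions or inflates PFS against an external benchmark. Those decisions count responses, no effect of later restaging on the counts has been shown, and the plan names no PFS benchmark.

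**The baseline scan.** A reader might infer from Section 3.4.3, and from "Baseline biopsies will be performed following patient enrolling on study" with no stated maximum gap to day 1, that the plan permits a stale baseline. It does not: Sections 10 and 11.1.3 both cap the scan at 4 weeks before treatment. Nor does the biopsy step apply to NSCLC patients, who are not biopsied (Section 9.2.3.1).

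**Conclusion.** The point holds as a cheap improvement of modest size. The plan gives two restaging rules that agree only when no cycle is delayed, and no rule for what to do when one is. If cycles govern, the first restaging can move from week 8 to week 10 or week 12, depending on when in the cycle the scan is done, and later intervals can reach 12 weeks. These figures assume the maximum toxicity delay each time and a 2-week limit that applies per delay. Mean recorded progression is then about 2 weeks later, given exponential progression and the assumed medians; with fewer or shorter delays the shift is smaller.

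The outcomes affected are the PFS rate, by an amount that depends on the unstated landmark, and the duration of response. No sample size, power or error figure in Section 13 depends on this. The baseline windows are a secondary matter of wording.

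**What to change.** In Sections 5, 10 and 11.1, use one rule: tumor imaging every 8 weeks counted from cycle 1 day 1, with a stated window (for example ±1 week), regardless of cycle delays, and every 12 weeks after one year. The intervals are the plan's own (2 and 3 undelayed cycles); the ±1 week is a suggestion with no source in the documents.

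In Section 3.4.3, count the 28 days back from start of treatment so that the screening window matches Sections 10 and 11.1.3.

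**Cost.** This is a wording amendment. Scheduled first-year scans are the baseline plus weeks 8, 16, 24, 32, 40 and 48: 1 + 6 = 7, the yearly maximum of CT scans given in Section 14.4. After a delay a scan may not coincide with a cycle visit. The optional restaging biopsy is tied to day 1 (±2 days) of the cycle after the triggering scan (Section 9.2.3.1 and calendar footnote f), so it may then fall further from that scan. The amendment should say whether that is acceptable.

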11.1.1 Definitions

Evaluable for toxicity: All patients will be evaluable for toxicity from the time of their first treatment with study drugs.

Evaluable for objective response: All patients who received study drug will be considered evaluable for assessment of response. These patients will have their response classified according to the definitions stated below. (Note: Patients who exhibit objective disease progression prior to the end of cycle 1 will also be considered evaluable.)

Evaluable Non-Target Disease Response: Patients who have lesions present at baseline that are evaluable but do not meet the definitions of measurable disease, have received at least one cycle of therapy, and have had their disease re-evaluated will be considered evaluable for non-target disease. The response assessment is based on the presence, absence, or unequivocal progression of the lesions.

11.1.2 Disease Parameters

Measurable disease: Measurable lesions are defined as those that can be accurately measured in at least one dimension (longest diameter to be recorded) as ≥ 20 mm by chest x-ray or as ≥ 10 mm with CT scan, MRI, or calipers by clinical exam. All tumor measurements must be recorded in millimeters (or decimal fractions of centimeters).

Malignant lymph nodes: To be considered pathologically enlarged and measurable, a lymph node must be ≥ 15 mm in short axis when assessed by CT scan (CT scan slice

thickness recommended to be no greater than 5 mm). At baseline and in follow-up, only the short axis will be measured and followed.

Non-measurable disease: All other lesions (or sites of disease), including small lesions (longest diameter <10 mm or pathological lymph nodes with ≥ 10 to < 15 mm short axis), are considered non-measurable disease. Bone lesions, leptomeningeal disease, ascites, pleural/pericardial effusions, lymphangitis cutis/pulmonitis, inflammatory breast disease, and abdominal masses (not followed by CT or MRI), are considered as non-measurable.

Note: Cystic lesions that meet the criteria for radiographically defined simple cysts should not be considered as malignant lesions (neither measurable nor non-measurable) since they are, by definition, simple cysts.

‘Cystic lesions’ thought to represent cystic metastases can be considered as measurable lesions, if they meet the definition of measurability described above. However, if non-cystic lesions are present in the same patient, these are preferred for selection as target lesions.

Target lesions: All measurable lesions up to a maximum of 2 lesions per organ and 5 lesions in total, representative of all involved organs, should be identified as **target lesions** and recorded and measured at baseline. Target lesions should be selected on the basis of their size (lesions with the longest diameter), be representative of all involved organs, but in addition should be those that lend themselves to reproducible repeated measurements. It may be the case that, on occasion, the largest lesion does not lend itself to reproducible measurement in which circumstance the next largest lesion which can be measured reproducibly should be selected. A sum of the diameters (longest for non-nodal lesions, short axis for nodal lesions) for all target lesions will be calculated and reported as the baseline sum diameters. If lymph nodes are to be included in the sum, then only the short axis is added into the sum. The baseline sum diameters will be used as reference to further characterize any objective tumor regression in the measurable dimension of the disease.

Non-target lesions: All other lesions (or sites of disease) including any measurable lesions over and above the 5 target lesions should be identified as **non-target lesions** and should also be recorded at baseline. Measurements of these lesions are not required, but the presence, absence, or in rare cases unequivocal progression of each should be noted throughout follow-up.

